9.3.2.2.3 Sensitivity Analysis

Not applicable because the primary endpoints are safety and tolerability assessments.

9.4 Safety Analysis

Part A and Part B

Safety is a secondary objective of Part A, and the primary objective of Part B. All safety analyses will be conducted for Part A and Part B separately, based on data from the corresponding TE period in the Safety Set.

The overall safety profile of study drug will be assessed in terms of the following safety and tolerability endpoints:

- Treatment-emergent adverse events (TEAEs)
- Clinical laboratory values
- Standard 12-lead ECGs
- Vital signs
- Pulse oximetry

Only descriptive analysis of safety will be performed, and no statistical testing will be performed.

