### 9.2 Method of Assigning Subjects to Treatment Groups

This is an open-label study. Randomization is not required because all subjects will be treated identically. An interactive web response system (IWRS) will be used to dispense dosage based on subject weight at Day 1.

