**Part A**

The VX-445 dose of 100 mg qd selected for evaluation in Part A was determined based on population-PK modeling utilizing data from adults and simulating exposures over a range of

body weights typical for a population of 6- to <12-year-olds, ranging from 15 to 50 kg. The simulations indicate that a VX-445 dose of 100 mg qd is predicted to provide exposures that would not exceed the exposures observed in adults dosed with 200 mg qd. Hence, the VX-445 100-mg qd dose was predicted to be safe and was selected to be evaluated in Part A for all subject weight groups.

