## **Part B**

For Part B, subjects in the higher weight range will be administered VX-445 200 mg qd. The appropriate weight cutoff for the switch from 100 mg qd to 200 mg qd was determined based on population-PK modeling which was updated with preliminary PK data from Part A and data from studies conducted in adult and adolescent CF subjects. For Part B, a VX-445 dose of 100 mg qd will be evaluated in subjects weighing <30 kg. In subjects weighing  $\geq 30$  kg, a VX-445 dose of 200 mg qd will be evaluated. These doses are predicted to be safe based on PK data from Part A, data obtained from adults in the Phase 2 Study 445-001, and preliminary data obtained from adults and adolescents (12- to <18-year-olds) in Phase 3 Studies 445-102 and 445-103.

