## **TEZ and IVA Dosages**

TEZ will be administered as 50 mg qd and IVA will be administered as 75 mg every 12 hours (q12h) in all subjects in Part A and in subjects weighing <30 kg in Part B. In Part B, doses of TEZ 100 mg qd and IVA 150 mg q12h will be administered in subjects weighing  $\geq 30$  kg. The dosages and weight cutoff in Part B were selected based on an evaluation of PK and safety of TEZ/IVA in CF subjects 6 to 11 years of age in Part A of Study VX15-661-113 (Study 661-113). Part B of Study 661-113 assessed the safety and efficacy of TEZ/IVA at these doses in CF subjects 6 to 11 years of age.

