9.2.2 Demographics and Baseline Characteristics

Part A and Part B

Demographics and baseline characteristics will be summarized based on the FAS.

Demographic data will include the following:

- Age at baseline (in years)
- Sex (male, female)
- Ethnicity (Hispanic or Latino, not Hispanic or Latino, and not collected per local regulations)

- Race (White, Black or African American, Asian, American Indian or Alaska Native, Native Hawaiian or Other Pacific Islander, Other, and not collected per local regulations)
- Geographic region (North America for Part A; North America, Europe [including Australia] for Part B)

Baseline characteristics will include the following:

- CFTR genotype group (F/F, F/MF)
- Weight group (<30 kg, and ≥ 30 kg)
- Weight (kg)
- Weight z-score
- Height (cm)
- Height z-score
- BMI (kg/m^2)
- BMI z-score

Disease characteristics will include the following:

- ppFEV₁ at baseline (<70, ≥ 70 to ≤ 90 , and >90)
- ppFEV₁ at baseline (continuous)
- Sweat chloride at baseline (continuous)

For Part B, the following additional disease characteristics will also be provided:

- CFQ-R respiratory domain score at baseline (child's version; continuous)
- LCI_{2.5} at baseline (continuous)
- Prior use of CFTR modulator (Yes, No)
- Prior use of dornase alfa (Yes, No)
- Prior use of azithromycin (Yes, No)
- Prior use of inhaled antibiotic (Yes, No)
- Prior use of any bronchodilator (Yes, No)
- Prior use of any inhaled bronchodilator (Yes, No)
- Prior use of any inhaled hypertonic saline (Yes, No)
- Infection with *Pseudomonas aeruginosa* within 2 years prior to screening (Positive, Negative)

In addition, the following data listings will also be provided:

- Informed consent/assent;
- Inclusion/Exclusion criteria violation for subjects with any such violations.

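### Part B safety summaries are not split by the two weight-based regimens, so the tables as specified describe neither regimen on its own

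*SAP*

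**What the plan says.** Protocol 9.2 sets the regimen by weight: "An interactive web response system (IWRS) will be used to dispense dosage based on subject weight at Day 1". Protocol Table 9-1 and SAP Table 7-1 give the two Part B regimens. Below 30 kg it is VX-445 100 mg qd, TEZ 50 mg qd and IVA 75 mg q12h. At 30 kg and above it is 200 mg qd, 100 mg qd and 150 mg q12h.

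Part A used only the lower of these. Protocol 9.3.3 says of it that "the VX-445 100-mg qd dose was predicted to be safe and was selected to be evaluated in Part A for all subject weight groups", and gives TEZ and IVA in Part A at the lower level too. For Part B the same section says that "subjects in the higher weight range will be administered VX-445 200 mg qd".

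Safety is the primary objective of Part B. The only division of the safety analyses stated in SAP 9.4 is by study part: "All safety analyses will be conducted for Part A and Part B separately". The subsections then organise the output as follows:

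- adverse events by system organ class and preferred term, relationship and severity (9.4.1)
- laboratory results by visit and threshold category, with liver scatter plots for Part B (9.4.2)
- ECG and vital signs by visit and threshold, and pulse oximetry by visit and shift from baseline (9.4.3 to 9.4.5)

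None of these mentions weight group or dose, and neither does Protocol 12.3.4. The grouping variable exists, but SAP 9.2.2 lists it only among the baseline characteristics: "Weight group (<30 kg, and ≥ 30 kg".

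SAP 7.2 and Table 7-2 give the chance of seeing at least one subject with an event for 45 and 50 subjects, without reference to regimen.

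**The concern.** The primary question in Part B is how safe and tolerable the treatment is as given, and it is given as two regimens. A percentage taken over both groups describes neither of them. If an event occurs only, or mainly, in one group, the pooled percentage understates its frequency there, and the planned tables would not show that the groups differ.

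This matters more for the ≥30 kg group, because Part A gives no safety data on its regimen. The sample-size statement also invites a reader to carry its 90% over to each regimen, although it was calculated for all subjects together.

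**Working it through.** **Inputs.** Planned enrolment is about 56, with about 45 expected to complete (SAP 7.2). The Safety Set is everyone who receives at least one dose (SAP 8.2), so about 56 is the relevant denominator for the safety tables. The documents do not state how many children weigh 30 kg or more. I assume a share of 20% to 50% and show the range.

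**Step 1: reproduce Table 7-2.** The formula is P(at least 1 event) = 1 − (1 − θ)^n.

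- n = 45: 1 − 0.95^45 = 90.06% and 1 − 0.90^45 = 99.13%; the table has 90.0% and 99.1%.
- n = 50: 92.31% and 99.48%; the table has 92.3% and 99.5%.

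All four figures agree, so the table is right for the pooled group. At n = 56 the values are 94.3% and 99.7%.

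**Step 2: the same formula for the ≥30 kg group alone, and the dilution.** The pooled rate is the group rate × (group n / 56), with no events in the lighter group. The last column takes a 20% rate confined to the heavier group.

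| Assumed share | ≥30 kg, of 56 | P(≥1) at 5% | P(≥1) at 10% | 20% rate shows pooled as |
|---|---|---|---|---|
| 20% | 11 | 43.1% | 68.6% | 3.9% |
| 30% | 17 | 58.2% | 83.3% | 6.1% |
| 40% | 22 | 67.6% | 90.2% | 7.9% |
| 50% | 28 | 76.2% | 94.8% | 10.0% |

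With a share of exactly 40%, the dilution is 0.40 × 20% = 8%; the table has 7.9% because 22/56 is 39.3%. Counting only 45 completers (9 to 22 children) would give 37% to 68% at 5% incidence.

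**Step 3: an example of what the table would show.** Suppose 22 of 56 children weigh 30 kg or more and 4 have an event that no lighter child has.

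- By group: 4/22 = 18.2%, exact 95% CI 5.2% to 40.3%.
- Pooled: 4/56 = 7.1%, exact 95% CI 2.0% to 17.3%.

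The pooled interval does not reach the rate observed in the group where the events occurred.

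**What each step measures.** Step 2's detection probabilities depend on how many children are in the group and are the same whatever the table layout. The dilution in the last column of step 2 and in step 3 is what the layout causes and what separate columns would remove.

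**The case against.** The case on the other side has several parts.

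- **Evidence outside the study.** A reader might infer that Part B is the only evidence on the higher regimen. The documents do not support that. Protocol 9.3.3 cites VX-445 200 mg qd in Phase 2 and in Phase 3 subjects aged 12 and over, and TEZ/IVA at the Part B doses in children aged 6 to 11. What stands is narrower: within this study, only Part B gives the triple combination at that regimen in this age group.
- **Doubling in milligrams is not doubling per kilogram.** With the 15 kg entry minimum and the 15 to 50 kg range modelled in Protocol 9.3.3, VX-445 runs from 100/30 = 3.3 to 100/15 = 6.7 mg/kg below the cutoff, and from 200/50 = 4.0 to 200/30 = 6.7 mg/kg above it. The ranges largely overlap, and the cutoff came from population-PK modelling. So there is no ground for presuming the heavier group to be the high-toxicity group. The case for the split is that two regimens are given and each should be described.
- **Listings and the IDMC.** A reader might infer that a toxicity confined to one regimen could not be found at all. That goes too far. An event in a heavier child is still counted in the pooled table. Adverse events, laboratory values, ECGs and vital signs are listed by subject, and the IDMC reviews safety under a charter and analysis plan that are not among these documents. The SAP does not say that the listings carry regimen or weight group, and rebuilding a table by hand is not a planned summary of the primary endpoint. This mitigates the point in part.
- **Silence.** The SAP never says that the columns are pooled, and no table shells are visible. That is why the point is confined to what the visible text specifies.
- **Interpretability.** Regimen is fixed by weight and so probably goes with age. Split columns cannot isolate a dose effect. This stands and limits how they may be read.

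**Conclusion.** The point holds as a gap in presentation. The visible text specifies no Part B safety summary by regimen, although the primary objective is safety, two regimens are given, and the grouping variable is already defined.

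The size depends on the unstated share of children at 30 kg or more. For shares of 20% to 50% of about 56, a 20% event rate confined to that group would show as about 4% to 10% in a pooled table. Over the same range, the chance of seeing at least one event of 5% incidence in that group is about 43% to 76%, against the 90% stated for 45 subjects together.

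A reader might infer that adding columns would restore the 90%. It would not: that limit comes from group size. Nor does the gap make any planned result invalid; the pooled figures remain correct for the mixture of children enrolled.

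**What to change.** In SAP 9.4, present the main Part B safety tables in three columns (<30 kg, ≥30 kg and total) with Safety Set denominators. The tables are the TEAE overview, the system organ class and preferred term tables, the liver thresholds, and the ECG and vital-sign thresholds. State that the columns are descriptive and that regimen is confounded with weight and probably age.

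Beside SAP Table 7-2 (and Protocol Table 12-1, if it is amended), note that the probabilities are for the pooled group, and give the per-group range with its assumed shares. If a split by regimen is already intended in the table shells, one sentence in 9.4 saying so would settle this part.

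The statement in Protocol 9.2 that all subjects are treated identically should also be reconciled with the weight-based dispensing described in the next sentence.

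The cost is SAP wording and two extra columns on a variable that SAP 9.2.2 already defines. SAP 4 says that version 3.0 is to be approved before the Part B data lock, so the split can be pre-specified. SAP 9.4 plans no safety testing, so no multiplicity issue arises, and nothing in treatment or data collection changes. The downside is small counts per column.

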9.4.1 Adverse Events

Part A and Part B

For analysis purposes, AEs will be classified as pretreatment AEs, TEAEs, or post-treatment AEs, defined as follows:

- **Pretreatment AE:** any AE that occurred before the first dose date of study drug in the corresponding Part.

- **TEAE:** any AE that worsened (either in severity or seriousness) or that was newly developed at or after the first dose of study drug through the end of the TE period in the corresponding Part.
- **Extended TEAE: (Part B only)** any AE that worsened (either in severity or seriousness) or that was newly developed at or after the first dose of study drug in Part B through the end of the Extended Treatment-emergent Period.
- **Post-treatment AE:** any AE that worsened (either in severity or seriousness) or that was newly developed after the TE period in the corresponding Part.

For AEs with completely missing or partially missing start dates, if there is no clear evidence that the AEs were pretreatment or post-treatment, the AEs will be classified as TEAEs.

Details for imputing missing or partial start dates of adverse events are defined in [Appendix D](#).

An overview of all TEAEs will be provided with the following categories:

- Number of TEAEs (total number of TEAEs only)
- Subjects with any TEAEs
- Subjects with TEAEs by strongest relationship
- Subjects with TEAEs by maximum severity
- Subjects with TEAEs leading to study drug discontinuation (discontinuation of any study drug)
- Subjects with TEAEs leading to study drug interruption (interruption of any study drug)
- Subjects with grade 3/4 TEAEs
- Subjects with related TEAEs
- Subjects with serious TEAEs
- Subjects with related serious TEAEs
- Subjects with TEAEs leading to death

The following summary tables of TEAEs will be presented:

- All TEAEs
- TEAEs leading to treatment discontinuation
- TEAEs leading to treatment interruption
- Serious TEAEs
- TEAEs leading to death
- Grade 3/4 TEAEs
- TEAEs by strongest relationship
- TEAEs by maximum severity

- Related TEAEs
- Related serious TEAEs (Part B only)

Summaries will be presented by MedDRA SOC and PT using frequency counts and percentages (i.e., number and percentage of subjects with an event). When summarizing the number and percentage of subjects, subjects with multiple occurrences of the same AE or a continuing AE will be counted once and only the maximum severity level will be presented in the severity summaries, and the strongest relationship level will be presented in the relationship summaries.

Additional summary tables will be provided for TEAEs showing number and percentage of subjects

- All TEAEs by PT

All AEs, including pretreatment AEs, TEAEs, and post-treatment AEs, will be presented in an individual subject data listing based on the All Subjects Set. In addition, a listing containing individual subject adverse event data for TEAEs leading to treatment discontinuation, TEAEs leading to treatment interruption, Grade 3/4 TEAEs, SAEs and all deaths will be provided separately, with a flag indicating the TEAE status for SAEs and deaths.

9.4.2 Clinical Laboratory

Part A and Part B

For the treatment-emergent laboratory assessments, the observed values and change from baseline values of the continuous hematology, coagulation and chemistry results will be summarized in SI units at each visit.

The number and percentage of subjects meeting at least 1 threshold analysis criterion event for selected parameters during the TE period will be summarized. The threshold analysis criterion shift from baseline will also be summarized for selected laboratory parameters. The threshold analysis criteria are provided in [Appendix E](#).

Results of urinalysis and the positive urine/serum pregnancy test will be listed in individual subject data listings only. For positive serum pregnancy listing, subjects with serum HCG which are abnormal will be selected.

In addition, a listing containing individual subject hematology, chemistry, and coagulation values will be provided. This listing will include data from both scheduled and unscheduled visits.

Part B Only

For selected LFT laboratory tests (alanine transaminase [ALT], aspartate transaminase [AST], alkaline phosphatase [ALP], and total bilirubin), a scatter plot of the maximum treatment-emergent value versus the baseline value corresponding to \times ULN (upper limit of normal) will be presented. Further, a scatter plot of the maximum treatment-emergent value of ALT and AST, separately, versus the maximum treatment-emergent value of total bilirubin corresponding to \times ULN will also be presented.

9.4.3 Electrocardiogram

Part A and Part B

For the treatment-emergent ECG measurements, a summary of observed values and change from baseline values will be provided at each visit for the following ECG measurements (in msec): RR interval, PR interval, QT interval, QTcF interval, QRS duration, and Heart Rate (beats per minute).

The number and percentage of subjects meeting at least 1 threshold analysis criterion for selected parameters during the TE period will be summarized. The threshold analysis criteria are provided in [Appendix E](#).

In addition, a listing containing individual subject ECG values will be provided. This listing will include data from both scheduled and unscheduled visits.

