**Table 3-4 VX18-445-106, Part B Treatment Period and Safety Follow-up Visit**

Event/ Assessment a	Day 1	Day 3 (± 1 day)	Day 15 (± 3 days)	Week 4 (± 5 days)	Week 8 (± 5 days)	Week 12 (± 5 days)	Week 16 (± 5 days)	Week 20 (± 5 days)	Week 24 (± 5 days)	ETT Visit	Safety Follow-up Visit 28 (± 7) Days After the Last Dose of Study Drug b	Comments
Pulse Oximetry	X		X	X	X	X	X		X	X	X	Collected after the subject has been at rest for at least 5 minutes (Section 11.5.3).
Standard 12-lead ECG	X		X		X	X	X		X	X	X	Performed after the subject has been at rest for at least 5 minutes and before the AM dose (Section 11.5.4).
Spirometry	X		X	X	X	X	X		X	X	X	Should be performed pre-bronchodilator, before the AM dose, and at approximately the same time at each visit (Section 11.4.1).
Sweat chloride	X		X	X		X			X	X		Section 11.4.2
Pregnancy Test (all female subjects)	X (urine)			X (serum)	X (serum)	X (serum)	X (serum)	X (serum)	X (serum)	X (serum)	X (serum)	A local laboratory may be used for the Week 20 sample if a subject cannot return to the study site for the blood draw (Section 11.5.2).
Serum Chemistry	X		X	X	X	X	X	X	X	X	X	Section 11.5.2 for details. Liver function testing (ALT, AST, GGT, ALP, and total bilirubin) must be performed at the scheduled visits and at Week 20 (a minimum of every 4 weeks after Week 4). A local laboratory may be used for the Week 20 sample if a subject cannot return to the study site for the blood draw.
Hematology	X		X	X	X	X	X		X	X	X	Section 11.5.2 for details.
Coagulation	X								X	X	X	Section 11.5.2 for details.
Urinalysis	X								X	X	X	Section 11.5.2 for details.

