- In the derivation of maximum and minimum values during TE periods, and maximum and minimum change from baseline values during TE periods for safety analyses
- In individual subject data listings as appropriate

Visit windowing rules: For analysis specified in Sections 9.2, 9.3, and 9.4, the analysis visit windows for protocol-defined visits are provided in [Appendix A](#).

Incomplete/missing data will not be imputed, unless specified otherwise.

Outliers: No formal statistical analyses will be performed to detect or remedy the presence of statistical outliers, unless specified otherwise.

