12 LIST OF APPENDICES

▪ Appendix A: Analysis Visit Windows for Safety and Efficacy Assessments

Table 12-1 Analysis Visit Windows for Safety and Efficacy Assessments in Part A			
Assessment	Visit¹	Target Study Day	Analysis Visit Window (in study days)^{2, 3, 4}
Safety Assessment			

 • Serum Chemistry • Hematology 	Day 1 (Baseline)	1	≤1 Pre-dose
	Day 8	8	[1, 12]
	Day 15	15	(12, 29]
	Safety Follow-up	Not applicable	Use nominal visit

 • Standard 12-lead ECG 	Day 1 (Baseline)	1	≤1 Pre-dose
	Day 2	2	[1, 9]
	Day 15 Pre-dose and Post-dose	Not applicable	Use nominal visit
	Safety Follow-up	Not applicable	Use nominal visit

 • Vital Signs 	Day 1 (Baseline)	1	≤1
	Day 2	2	[1, 5]
	Day 8	8	(5, 12]
	Day 15	15	(12, 29]
	Safety Follow-up	Not applicable	Use nominal visit

 • Coagulation 	Day 1 (Baseline)	1	≤1 Pre-dose
	Day 15	15	[1, 29]
Efficacy Assessment and Pharmacodynamic Assessment			

 • Spirometry 	Day 1 (Baseline)	1	≤1 Pre-dose
	Day 2	2	(1, 5]
	Day 8	8	(5, 12]
	Day 15	15	(12, 29]
	Safety Follow-up	Not applicable	>29

 • Sweat Chloride 	Day 1 (Baseline)	1	≤1 Pre-dose
	Day 15	15	(1, 29]

 • Weight, Height and BMI (and the corresponding z-scores, as applicable) 	Day 1 (Baseline)	1	≤1
	Day 15	15	(1, 29]
	Safety Follow-up	Not applicable	>29

Table 12-2 Analysis Visit Windows for Safety and Efficacy Assessments in Part B			
Assessment	Visit¹	Target Study Day	Analysis Visit Window (in study days)^{2, 3, 4}
Safety Assessment			
• Serum Chemistry	Day 1 (Baseline)	1	≤1 Pre-dose
	Day 15	15	[1, 22]
	Week 4	29	(22, 43]
	Week 8	57	(43, 71]
	Week 12	85	(71, 99]
	Week 16	113	(99, 127]
	Week 20	141	(127, 155]
	Week 24	169	(155, 183]
	Safety Follow-up	Not applicable	Use nominal visit
• Hematology	Day 1 (Baseline)	1	≤1 Pre-dose
	Day 15	15	[1, 22]
	Week 4	29	(22, 43]
	Week 8	57	(43, 71]
	Week 12	85	(71, 99]
	Week 16	113	(99, 141]
	Week 24	169	(141, 183]
		Safety Follow-up	Not applicable
• Vital Signs (excluding weight, height, and BMI)	Day 1 (Baseline)	1	≤1
	Day 15	15	[1, 22]
	Week 4	29	(22, 43]
	Week 8	57	(43, 71]
	Week 12	85	(71, 99]
	Week 16	113	(99, 141]
	Week 24	169	(141, 183]
		Safety Follow-up	Not applicable
• Standard 12-lead ECG	Day 1 (Baseline)	1	≤1 Pre-dose
	Day 15	15	[1, 50]
	Week 12	85	(50, 99]
	Week 16	113	(99, 141]
	Week 24	169	(141, 183]

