		Safety Follow-up	Not applicable
• Coagulation	Day 1 (Baseline)	1	≤1 Pre-dose
	Week 24	169	[1, 183]
	Safety Follow-up	Not applicable	Use nominal visit
Efficacy Assessment and Pharmacodynamic Assessment			
• Spirometry	Day 1 (Baseline)	1	≤1 Pre-dose
	Day 15	15	(1, 22]
	Week 4	29	(22, 43]
	Week 8	57	(43, 71]
	Week 12	85	(71, 99]
	Week 16	113	(99, 141]
	Week 24	169	(141, 183]
		Safety Follow-up	Not applicable

Table 12-2 Analysis Visit Windows for Safety and Efficacy Assessments in Part B			
Assessment	Visit¹	Target Study Day	Analysis Visit Window (in study days)^{2, 3, 4}

 Weight, Height and BMI (and the corresponding z-scores) 	Day 1 (Baseline)	1	≤1
	Day 15	15	(1, 22]
	Week 4	29	(22, 43]
	Week 8	57	(43, 71]
	Week 12	85	(71, 99]
	Week 16	113	(99, 141]
	Week 24	169	(141, 183]
	Safety Follow-up	Not applicable	>183

 Modified Facial Hedonic Scale 	Day 1	1	≤1
	Day 15	15	(1, 22]
	Week 4	29	(22, 43]
	Week 8	57	(43, 71]
	Week 12	85	(71, 99]
	Week 16	113	(99, 141]
	Week 24	169	(141, 183]
	Safety Follow-up	Not applicable	>183

 CFQ-R 	Day 1 (Baseline)	1	≤1
	Week 4	29	(1, 43]
	Week 8	57	(43, 71]
	Week 12	85	(71, 99]
	Week 16	113	(99, 141]
	Week 24	169	(141, 183]
	Safety Follow-up	Not applicable	>183

 Sweat Chloride Lung Clearance Index 	Day 1 (Baseline)	1	≤1 Pre-dose
	Day 15	15	(1, 22]
	Week 4	29	(22, 57]
	Week 12	85	(57, 127]
	Week 24	169	(127, 183]

Notes:

¹ Visit name for analysis purpose is used to report data in tables and figures.

² The analysis visit windows will be applied using the following rules for both scheduled and unscheduled visits:

- If no numerical measurement is available within a visit window, the measurement will be considered missing for the visit.
- If there is more than 1 numerical measurement available within a visit window, use the following rules:
 - The measurement closest to the target day will be used; or
 - If there are multiple measurements with the same distance from the target day, the latest measurement will be used. If the latest measurement cannot be determined, then unscheduled visit will be selected

³ For measurements collected on the date of first dose of study drug, if it cannot be determined whether the measurement is before or after the first dose:

- a. Scheduled measurement will be treated as pre-dose observation.
- b. Unscheduled measurement will be treated as post-dose observation.

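### The Part B ECG analysis windows omit Week 8, so the scheduled Week 8 ECGs either drop out of the by-visit summary or are tabulated as Week 12

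*SAP*

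**What the plan says.** Protocol Table 3-4 schedules Part B ECGs at Day 1, Day 15, Weeks 8, 12, 16 and 24, the ETT Visit and the Safety Follow-up Visit. There is none at Day 3, Week 4 or Week 20. Protocol 12.3.4.3 commits to ECG summaries at every scheduled visit. In SAP 9.4.3, "a summary of observed values and change from baseline values will be provided at each visit for the following ECG measurements".

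SAP 9.1 says that, for the analyses in Sections 9.2 to 9.4, "the analysis visit windows for protocol-defined visits are provided in" Appendix A. The Part B table there, Table 12-2 ("Analysis Visit Windows for Safety and Efficacy Assessments in Part B"), gives these post-baseline ECG windows: Day 15 [1, 50], Week 12 (50, 99], Week 16 (99, 141] and Week 24 (141, 183], with Safety Follow-up handled separately. It has no Week 8 row for ECG.

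Two notes to the table decide what happens to a Week 8 ECG. Note 1 says "Visit name for analysis purpose is used to report data in tables and figures". Note 2 says that when several values fall in one window, "The measurement closest to the target day will be used".

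**The concern.** Standard 12-lead ECGs are a named component of the Part B primary endpoint (protocol 7.1, SAP 6.1). The protocol asks for a Week 8 ECG from every subject and promises a summary at each scheduled visit, but the SAP has nowhere to put it. The values are not left unassigned. They fall in a neighbouring window, where they are either discarded or shown under the wrong visit name. The Week 12 column for heart rate, PR, QRS, QT and QTcF could then mix values taken about four weeks apart, with nothing in the table to show it.

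The gap is specific to ECG. Serum chemistry, hematology, vital signs, spirometry, weight/height/BMI, the Modified Facial Hedonic Scale and CFQ-R are all scheduled at Week 8, and all have a Week 8 window of (43, 71]. Sweat chloride and LCI have no Week 8 window, correctly, because the protocol schedules neither then.

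**Working it through.** **Inputs.** Target days from SAP Table 12-2: Day 15 = 15, Week 8 = 57 (from the other assessments), Week 12 = 85, Week 16 = 113, Week 24 = 169. Visit tolerance from protocol Table 3-4: ± 5 days for Weeks 8 and 12.

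**Step 1: reproduce the SAP's cut-points.** The rule is the midpoint of consecutive target days, (a + b)/2.

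| Assessment | Targets used | Midpoints | Cuts in Table 12-2 |
|---|---|---|---|
| ECG, without Week 8 | 15, 85, 113, 169 | 50, 99, 141 | 50, 99, 141 |
| Hematology | 15, 29, 57, 85, 113, 169 | 22, 43, 71, 99, 141 | 22, 43, 71, 99, 141 |
| Sweat chloride, LCI | 15, 29, 85, 169 | 22, 57, 127 | 22, 57, 127 |

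The rule reproduces all three sets exactly. The ECG cuts come out only if Week 8 is left out: (15 + 85)/2 = 50. A row lost when the PDF was read cannot explain this, because the Day 15 and Week 12 windows meet at Day 50 and leave no room for one.

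**Step 2: place the Week 8 ECG.** Day 57 ± 5 gives Days 52 to 62. All 11 days exceed 50 and are below 99, so all fall in the Week 12 window.

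**Step 3: apply the closest-to-target rule.**
- Distance of a Week 8 ECG from Day 85: 85 − 62 = 23 to 85 − 52 = 33 days.
- Distance of an on-time Week 12 ECG (Days 80 to 90): at most 5 days.
- Across the 11 × 11 = 121 combinations of Week 8 and on-time Week 12 days, the Week 8 value is selected in 0.
- A Week 12 ECG as late as Day 99 is 99 − 85 = 14 days off target and still displaces it.
- If no ECG in the window is closer to Day 85, the Week 8 value is selected and labelled Week 12.

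**Step 4: rebuild the windows with Week 8.** (15 + 57)/2 = 36 and (57 + 85)/2 = 71; the cuts at 99 and 141 do not change. Days 52 to 62 then all lie in (36, 71].

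**Size.** One of five scheduled on-treatment post-baseline ECG visits is affected: 1/5 = 20%. If each subject has a Week 8 ECG, that is about 45 (expected completers) to 56 (planned enrollment) recordings. The documents give no Week 8 attendance figure, so this range is an assumption.

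A side effect is that an unscheduled ECG on Days 37 to 50 is assigned to Day 15 although it lies nearer to Day 57.

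**The case against.** The strongest counter-argument is that little depends on this. Part B safety is descriptive, with no testing (SAP 9.4). The threshold analysis uses every reported ECG value (SAP Appendix A, derived variable 5), and the ECG listing covers scheduled and unscheduled recordings (SAP 9.4.3). Clinically significant ECG abnormalities are recorded as AEs, and a QTcF above the protocol's limits triggers repeat recordings (protocol 11.5.4). No extreme value is lost, and by-visit means remain at Day 15 and Weeks 12, 16 and 24. This stands, and it confines the problem to the by-visit summaries.

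The relabelling is also conditional: it needs a Week 12 ECG that is missing or falls outside the window. The documents do not say how often that would happen. The COVID-19 addendum recognises that some subjects cannot travel, but it also allows ECGs at home, so the frequency cannot be estimated. This stands too. The loss of the Week 8 summary, however, is not conditional: no by-visit table can carry a Week 8 column, whether or not Week 12 is attended.

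Finally, SAP 9.4.3 read alone could be satisfied by summarizing only the analysis visits listed in Table 12-2. That reading fails against protocol 12.3.4.3, which covers every scheduled visit, and against SAP 9.1, which ties the windows to protocol-defined visits. Neither document states that Week 8 ECGs were meant to be left out.

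**Conclusion.** The concern holds. Table 12-2 contradicts the protocol's ECG schedule and its commitment to summarize each scheduled visit. Followed as written, the SAP gives no Week 8 ECG summary and can place a Week 8 value in the Week 12 column, 23 to 33 days ahead of its labelled target. Threshold counts, AE reporting and listings are intact, so this should be corrected but does not threaten the overall safety assessment.

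The conclusion rests on Week 8 visits occurring within the protocol's ± 5 days and on Notes 1 and 2 to Table 12-2 being applied literally. The relabelling further requires that no ECG in the Week 12 window lies closer to Day 85.

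**What to change.** Add a Week 8 row (target Day 57) to the Part B ECG block of SAP Table 12-2 and recut the adjacent windows by the midpoint rule already in use:

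- Day 15: [1, 36]
- Week 8: (36, 71]
- Week 12: (71, 99]
- Week 16: (99, 141], unchanged
- Week 24: (141, 183], unchanged

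The cost is one table edit and one more visit in the ECG output, with no new data. SAP Section 4 allows for it: version 3.0 is to be finalized before the Part B data lock, and later revisions go through a further amendment. If leaving Week 8 out was deliberate, the SAP should say so, justify the departure from protocol 12.3.4.3, and prevent Week 8 values from being used as Week 12.
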